4.3 Subject Recruitment, Enrollment and Screening

Study personnel will recruit subjects by word-of-mouth. Study personnel will review whether the subjects meet the inclusion criteria (Section 4.1 of this document), based on review of their available medical records.

Dr. [REDACTED]' lab also keeps a list of prior research participants who were recruited as healthy adults for other research studies and who agreed to be contacted for future studies. Study personnel will review this list and if subjects fulfill the inclusion criteria they will be contacted via the phone, to consider participation in the study (see the attachment: Verbal and Phone Recruitment Script).

Eligible subjects will be thus approached by the study personnel and study will be explained in detail. If subjects show interest in participation, their contact information will be collected and forwarded to study team/study coordinator.

Subjects will sign IRB approved consent form when presenting to the CRTU for the research study. Informed consent may also be obtained via Ptrax digital signature capture technology on Mayo devices.

4.4 Early Withdrawal of Subjects

4.4.1 When and How to Withdraw Subjects

Subject participation in this study is completely voluntary. Subjects can withdraw their consent and discontinue participation in the study at any time without affecting their relationship with Mayo Clinic doctors or Mayo Clinic. Although we do not anticipate high withdrawal rates in our healthy study population, rare possible reasons for withdrawal from this protocol is if subject becomes suddenly concerned about the safety or side effects of the study drug. This type of

withdrawal could be prevented by clear disclosure of the potential side effects of Adderall to the subject prior to enrollment. However if such situation does occur, subject will be allowed to discontinue participation in the two day study protocol.

Subject participation in this study may be ended by the principal investigator if it is felt it is in the best interest of the subject, if subjects do not follow the study procedures, or if the study is stopped.

Subjects will not need to be replaced per-se; enrollment of subjects will continue until desired number of participants is completed. There is no long term follow up in this study protocol.

4.4.2 Data Collection and Follow-up for Withdrawn Subjects

If subjects inform the study team of their voluntary withdrawal from the study protocol, data obtained up to the moment of withdrawal from the study may be used in the analysis, unless subject notifies us otherwise.

This study is not designed to answer any long-term follow up questions.

5 Study Drug

5.1 Description

- Name of investigational drug: Dextroamphetamine and amphetamine
- Brand name: Adderall
- Oral Generic Adderall: total of 25 mg dose. This dose will be compounded by Pharmacy. The compounded dose will contain: [dextroamphetamine sulfate 6.25 mg, dextroamphetamine saccharate 6.25 mg, amphetamine aspartate monohydrate 6.25 mg, amphetamine sulfate 6.25 mg (equivalent to amphetamine base 15.73 mg)].

The study drug and placebo drugs will be prepared by the CRTU Pharmacists. The drugs will be given in a capsule form.

5.2 Treatment Regimen

Adderall 25 mg given orally, one time dose.

5.3 Method for Assigning Subjects to Treatment Groups

The proposed research study is a randomized, double-blind, placebo-controlled clinical trial. The randomization list will be computer generated. We will utilize a randomized block design, with a block size of 6, considering enrolling 30 subjects, each completing two study days. This assures balance between the treatment arms after each group of 6 subjects. Subjects and study personnel will be blinded to the nature of the pill administered on each study day.

Randomization will be performed by CTSA statistician. De-identified coded spreadsheet will be provided to the research pharmacist who will be distributing the drug/placebo.

5.4 Preparation and Administration of Study Drug

Study drug and placebo will be prepared and dispensed by the research pharmacist, [REDACTED] Pharm.D., R.Ph., or [REDACTED] colleagues from SMH Research Pharmacy, [REDACTED]. The study drug will be administered by the research team (blinded to the pill being administered) in identical dispensing cups.

5.5 Subject Compliance Monitoring

The study protocol involves oral ingestion of one study pill (Adderall vs placebo pill), at one time. Study subjects will be personally observed by the study team when subjects take the drug, to assure their compliance with study protocol.

5.6 Prior and Concomitant Therapy

No prior or concomitant medical therapy will be utilized.

5.7 Packaging

The study drug and placebo drug will be packaged in a capsule form, delivering 25 mg of Adderall vs placebo. The study drug and placebo drug will be supplied by the Research Pharmacy at SMH.

5.8 Masking/Blinding of Study

Both drug preparations will be dispensed by an independent Research Pharmacist and will be given to the subject by research personnel in identical cups so that neither participants nor study personnel are aware of which drug is being administered. Study personnel blinded to the study will give the participant the active vs placebo drug, according to the randomized, double-blind, placebo-control crossover design of this study.

Blinding will be maintained until completion of the analysis of data.

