5.9.4 Return or Destruction of Study Drug

Study drug will be supplied by the Mayo Clinic pharmacy on a one-to-one basis, rather than batches. In this respect we do not anticipate to have drugs remaining or drugs to return. At the completion of the study, there will be a final reconciliation of drug provided by the Mayo Clinic Pharmacy, drug dispensed, drug returns, and drug remaining. This reconciliation will be logged on the drug reconciliation form, signed and dated. Any discrepancies noted will be documented and investigated, prior to return or destruction of unused study drug. Drug destroyed on site will be documented in the study files.

6 Study Procedures

6.1 Visit 1

Two CRTU visits - minimum 5 days apart, maximum 3 months apart.

CRTU Day # 1

1. Subjects report to SMH CRTU at the already pre-scheduled appointment time. Participants should not eat at least 4 hours prior to coming to CRTU. Participant is reminded to avoid all stimulants including caffeine and alcohol 24 hours prior to the study.
2. CRTU personnel informs study personnel when the subject arrives at the CRTU.
3. Study personnel explain the research study to the participant and obtain written informed consent.
4. CRTU personnel will obtain height and weight of the participant.
5. CRTU personnel performs urine pregnancy test as needed (Urine collection #1). If the participant is pregnant, then the participant is unable to participate in the study, and will receive \$25.00 for their time. In all participants at least 100 ml of urine may be collected for future biomarker analysis at baseline
6. Study personnel verbally ask and record the responses to Cardiovascular Research Data Sheet including anthropometrics and bioimpedance measurements.

7. Participant will be asked to fill out the following questionnaires on a Mayo laptop or on paper. Some of these questionnaires may be administered more than once: Stimulant Intake Questionnaire, Berlin Questionnaire, Breakfast Questionnaire, Food Scale, Food Intake Questionnaire, Adult ADHD Self Report Checklist, Symptoms Questionnaire, Sleepiness Scale.
8. CRTU Staff will insert peripheral intravenous line into the forearm and blood draw #1 will be obtained after at least 30 minutes of supine resting.
9. Study personnel will obtain BP and HR measurements in supine position. Measurements will be taken every 1-3 minutes throughout the study.
10. Study personnel will be obtaining 12-lead ECG recording throughout the study.

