11. Study personnel will perform paced breathing test, details described in the IRB Protocol. Breathing will be measured by elastic bands around the chest and abdomen.
12. Baseline endothelial function test will be performed by the study team.
13. Study personnel will perform orthostatic BP and HR measurements.
14. Study personnel blinded to the study will give the participant the study drug vs placebo drug with a glass of water, according to the randomized, double-blind, placebo-control crossover design of this study.
15. Study subject will be asked to rest in sedentary or recumbent position for 3 hours.
16. CRTU Staff will do blood draw #2 after 30 minutes of supine resting, 3 hours after intake of active drug/placebo drug.
17. The 12-lead ECG recording continues on.
18. Study personnel will perform post-intervention paced breathing test, details described in the IRB Protocol. Breathing will be measured by elastic bands around the chest and abdomen.
19. Post intervention endothelial function test will be performed by the study team.
20. Post intervention ultrasound of the heart may be performed by the study team or echo lab personnel.
21. Study personnel will perform orthostatic BP and HR measurements.

22. Study personnel will describe the series of stress tests that will follow and BP, HR, ECG measurements will continue through the stress tests.
23. Study personnel will perform series of stress tests (physical, mental, and cold stress), details described in the IRB Protocol. During the stress tests continuous BP, HR and 12-lead ECG data will be recorded and will continue to be recorded the recovery time periods.

Participants will be allowed to eat, selecting meals from a prepared menu.

24. Study subjects will be scheduled a follow up appointment in the CRTU to be done within 2 months (minimum 5 days apart) but at the same time of the day; and will be dismissed home for the day.

6.2 Visit 2

CRTU Day # 2

1. Subjects report to SMH CRTU at the already pre-scheduled appointment time. Participants should not eat at least 4 hours prior to coming to CRTU. Participant is reminded to avoid all stimulants including caffeine and alcohol 24 hours prior to the study.
2. CRTU personnel informs study personnel when the subject arrives at the CRTU.
3. Study personnel explain the research plan for day #2 and answers any questions the participant may have.

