7.2 Statistical Methods

Descriptive Statistics

Univariate descriptive statistics and frequency distributions will be calculated, as appropriate for all variables. Baseline values for demographic, clinical, and outcome variables (primary and secondary) will be tabulated for both groups (i.e., study drug vs placebo drug). Data will be inspected before analysis for the need of transformations to reduce the possible impact of outliers in skewed distributions, and transformed accordingly. Distributions across subgroups used in randomization will also be compared to assess whether the randomization was successful in equalizing distributions of these prognostic variables across treatment groups. Putative prognostic variables that will be investigated through these descriptive analyses include variables such as BP, HR, age, gender, BMI, baroreflex sensitivity, catecholamine responses.

Handling of Missing Data

We expect missing data to be minimal. However, some subjects may drop out from the two study day protocol. The two-day longitudinal model is flexible to allow available data to be analyzed, for instance, if a subject completes the first study day, but not second study day. These models assume ignorable (MCAR/MAR) missingness. Sensitivity analyses may be performed to assess the robustness of these assumptions.

Multiplicity

There is no need to account for multiple comparisons in this study. With only 30 subjects, no correction for multiple comparisons using Bonferroni or Tukey's procedure will be necessary.

Primary Hypothesis: We hypothesize that BP and HR increase after intake of study drug compared to placebo.

Data will be analyzed using two-way analysis of variance (ANOVA) for repeated-measures with time (before vs after drug intake) as the within factor and group (study drug vs placebo drug) as the between factor. The key variable will be the group-by-time interaction. Differences in hemodynamics before and after consumption of a drug will be determined by repeated measures ANOVA. Student *t* test (paired or unpaired) will be used for between group comparisons with respect to change in given variable. $P < 0.05$ will be considered statistically significant. Data will be expressed as mean \pm SEM.

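### The blinding measures hide the pill but not its effect: no masked image reading is described for post-dose FMD, or for the heart ultrasound if the study team performs it

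*Combined protocol and SAP*

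**What the plan says.** - **Claimed blind.** Section 5.3: "Subjects and study personnel will be blinded to the nature of the pill administered on each study day". Section 5.8: "Blinding will be maintained until completion of the analysis of data".
- **Means described.** Sections 3.1, 5.3, 5.4 and 5.8 give similar capsules, identical cups, dispensing by an independent pharmacist, and a computer-generated list from the statistician that reaches the pharmacist as a coded sheet.
- **Who watches the signal.** Section 6.1, step 9: "Study personnel will obtain BP and HR measurements in supine position", and "Measurements will be taken every 1-3 minutes throughout the study". Section 6.2 repeats this for Day 2. The 12-lead ECG also runs throughout.
- **What the drug is expected to do.** Section 7.2: "We hypothesize that BP and HR increase after intake of study drug compared to placebo".
- **Who does the imaging.** Section 6.1, step 19: "Post intervention endothelial function test will be performed by the study team". Step 20: "Post intervention ultrasound of the heart may be performed by the study team or echo lab personnel". Section 6.2 has matching steps.
- **How FMD is set up.** Item 8 of the procedure list that closes section 6 inflates the forearm cuff to the subject's systolic BP plus 50 mmHg, capped at 200 mmHg.
- **Link between days.** Section 6.2, step 12: on Day 2 the subject gets whichever pill was not given on Day 1.
- **Allocation.** Section 5.3: "We will utilize a randomized block design, with a block size of 6".

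**The concern.** Matching capsules protect a blind only while the drug's effect stays out of sight of those who measure. Here the effect under test is on display to study personnel throughout, and FMD cannot be set up without the subject's systolic BP. In a two-period crossover, a guess about one day is also a guess about the other.

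FMD and heart function form secondary endpoint 6 (section 3.3), and section 1.1 states the expected direction, namely impairment. That placing and measuring an ultrasound image leaves room for operator judgement is general methodological knowledge, not a statement in the documents. If it is accepted, an operator or reader who suspects the active day could shift the result without intending to. A drug-placebo difference in FMD could then be ascribed in part to the observer, and nothing in the plan would answer that.

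**Working it through.** **1. Where knowledge could enter, in the order of section 6**

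- Day-1 baseline FMD precedes dosing, so no drug cue exists.
- Three hours of rest follow dosing. Taken literally, readings every 1-3 minutes give 180/3 = 60 to 180/1 = 180 BP and HR readings before post-dose testing.
- Post-dose FMD, then the optional heart ultrasound: the Day-1 response has been seen.
- Day-2 baseline FMD: a Day-1 guess carries over, because Day 2 is the other pill.
- Day-2 post-dose FMD, or any later reading of stored images: both days may have been seen.

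Sections 5.8, 6, 7.2 and 9.3 name no separate operator and no masked reader.

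**2. The plan's own figure**

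Section 7.1 takes rises of 5% and 1% with an SD of 5%: (5 - 1)/5 = 0.80 SD, which reproduces. It is used here as d, the size of the visible signal in one BP change. The 80% power attached to it is a separate matter, and nothing below depends on it.

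**3. Naming the pill from one day**

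Let the change be normal with equal SD on both pills and the means d SDs apart. Cutting at the midpoint gives P(correct) = Φ(d/2) = Φ(0.40) = 0.655.

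**4. Ordering the two days**

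The difference between a subject's two changes has mean d and SD √(2(1 - ρ)), where ρ is the within-subject correlation. So P(correct) = Φ(d/√(2(1 - ρ))).

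- ρ = 0: Φ(0.80/1.414) = Φ(0.566) = 0.714.
- ρ = 0.5: Φ(0.80/1) = 0.788.

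The documents give no ρ, so both values are assumptions. Larger effects, also assumed, show the range:

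| d (SD) | Day 1 only | Both days, ρ = 0 | Both days, ρ = 0.5 |
|---|---|---|---|
| 0.80 (section 7.1) | 65.5% | 71.4% | 78.8% |
| 1.0 (assumed) | 69.1% | 76.0% | 84.1% |
| 1.5 (assumed) | 77.3% | 85.6% | 93.3% |

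Chance is 50%. HR, ECG and visible stimulant effects are not counted, because the documents do not say how much they add to BP.

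**5. The block of 6**

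A 3:3 block has 20 possible arrangements. If every earlier sequence were known exactly, best guessing is right for 4.1 of 6 subjects (68.3%), and 1.5 of 6 (25%) are fully forced. That is an upper bound. With Day-1 guesses right 65.5% of the time, five in a row are all right with probability 0.655^5 = 0.12.

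A simulation of 20,000 blocks per setting let a best guesser use both days of every earlier subject in the block. With d = 0.80, knowing the block size moved Day-1 guessing from 65.8% to 67.0% (ρ = 0) and from 65.4% to 67.8% (ρ = 0.5). Both-day guessing moved from 71.5% to 72.3% and from 78.8% to 79.9%. Including d = 1.5, the gain was about 1 to 4 points.

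**The case against.** Some unblinding through effects is built into any comparison of a stimulant with an inert placebo. Frequent BP and HR readings are the primary endpoint, and section 3.1 calls this a pilot. All of that stands. It is a reason to protect the reading of images, because the exposure itself cannot be removed.

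The role labels are generic. Study personnel, study team and research team may be different people, and echo lab personnel may do the heart ultrasound. This stands too, and limits the firm case to FMD. But no text keeps the FMD operator away from the vitals, and the cuff setting requires systolic BP.

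Performing a scan is not reading it. Images are collected, and section 9.3 describes electronic capture and extraction, which is compatible with offline measurement. That shows masked reading is feasible, not that it is planned. The steps that refer the reader to the IRB protocol for detail are paced breathing and the stress tests, not FMD.

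A reader might infer more than the documents support:

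- **That the blind will probably fail.** At d = 0.80, between about one guess in five and one in three is wrong. Moreover, 0.80 is the effect the plan says it can detect, not one it predicts.
- **That the printed block size exposes the sequences.** The gain is about 1-4 points, and that staff know and use the block size is itself an inference.
- **That the stress and food results are equally open.** Handgrip is set by dynamometer at a fixed fraction of maximum for 2 minutes, arithmetic is timed, and the outcomes of both are BP and HR. Food is weighed by trained dietetic staff and analysed in software. Appetite and symptom ratings depend on what the subject feels, which masked image reading does not change.

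**Conclusion.** The concern holds for FMD, and for the heart ultrasound when the study team performs it. Section 5.8 asserts a blind to the end of analysis, yet for these images it is at risk and unprotected.

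The size is a guessing rate of about 66% after one day and 71-79% after both, against 50% by chance. It rests on normal changes, d = 0.80, an observer who sees BP and knows roughly where to cut, and an assumed ρ of 0 to 0.5. It says how often a guess would be right. It does not estimate a shift in FMD, and the documents offer no basis for one.

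The primary endpoint, read from devices, is not materially affected. The change is worth making because it is cheap, not because the main result is in doubt.

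**What to change.** In sections 5.8 and 6, state that FMD clips and any heart ultrasound clips are stored and then measured offline by the existing team from coded, shuffled files. The files should carry no subject identifier, treatment, study day, pre/post label or vitals. The code should be held by someone who does not measure, until the measurements are final.

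The cost is file coding and later reading. No extra procedure or outside reader is needed. Acquisition stays exposed, and a moving clip can still show heart rate, so the protection is partial.

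Two small additions are optional, and the point does not depend on them:

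- Undisclosed, varying block sizes for subjects not yet randomized. This removes at most the 1-4 point gain and costs a regenerated list.
- A recorded treatment guess from subject and operator on each day, reported as description only. Correct guesses can follow from a real drug effect, so the record cannot separate expectation from pharmacology.

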5.9 Receiving, Storage, Dispensing and Return

5.9.1 Receipt of Drug Supplies

Adderall will be obtained from Mayo Clinic/St. Marys Hospital Pharmacy, which will provide the drug to the Research Pharmacy at St. Marys Hospital. The drug will be verified by the pharmacist and drug receipt log will be kept by the pharmacy as well. Any discrepancies, damaged or unusable study drug (active drug or placebo) will be documented in the study files. The Principal Investigator of the study will be notified immediately of any discrepancies, damaged or unusable products.

5.9.2 Storage

Adderall and placebo drugs will be stored in a safe, dry place, protected from light, at room temperature (20-25 C), according to the recommendation published.

5.9.3 Dispensing of Study Drug

Regular study drug reconciliation will be performed by the research pharmacist to document drug assigned, drug dispensed, drug returns, and drug remaining. This reconciliation will be logged on the drug reconciliation form, and signed and dated by the research pharmacist.

5.9.4 Return or Destruction of Study Drug

Study drug will be supplied by the Mayo Clinic pharmacy on a one-to-one basis, rather than batches. In this respect we do not anticipate to have drugs remaining or drugs to return. At the completion of the study, there will be a final reconciliation of drug provided by the Mayo Clinic Pharmacy, drug dispensed, drug returns, and drug remaining. This reconciliation will be logged on the drug reconciliation form, signed and dated. Any discrepancies noted will be documented and investigated, prior to return or destruction of unused study drug. Drug destroyed on site will be documented in the study files.

6 Study Procedures

6.1 Visit 1

Two CRTU visits - minimum 5 days apart, maximum 3 months apart.

CRTU Day # 1

1. Subjects report to SMH CRTU at the already pre-scheduled appointment time. Participants should not eat at least 4 hours prior to coming to CRTU. Participant is reminded to avoid all stimulants including caffeine and alcohol 24 hours prior to the study.
2. CRTU personnel informs study personnel when the subject arrives at the CRTU.
3. Study personnel explain the research study to the participant and obtain written informed consent.
4. CRTU personnel will obtain height and weight of the participant.
5. CRTU personnel performs urine pregnancy test as needed (Urine collection #1). If the participant is pregnant, then the participant is unable to participate in the study, and will receive \$25.00 for their time. In all participants at least 100 ml of urine may be collected for future biomarker analysis at baseline
6. Study personnel verbally ask and record the responses to Cardiovascular Research Data Sheet including anthropometrics and bioimpedance measurements.

7. Participant will be asked to fill out the following questionnaires on a Mayo laptop or on paper. Some of these questionnaires may be administered more than once: Stimulant Intake Questionnaire, Berlin Questionnaire, Breakfast Questionnaire, Food Scale, Food Intake Questionnaire, Adult ADHD Self Report Checklist, Symptoms Questionnaire, Sleepiness Scale.
8. CRTU Staff will insert peripheral intravenous line into the forearm and blood draw #1 will be obtained after at least 30 minutes of supine resting.
9. Study personnel will obtain BP and HR measurements in supine position. Measurements will be taken every 1-3 minutes throughout the study.
10. Study personnel will be obtaining 12-lead ECG recording throughout the study.
11. Study personnel will perform paced breathing test, details described in the IRB Protocol. Breathing will be measured by elastic bands around the chest and abdomen.
12. Baseline endothelial function test will be performed by the study team.
13. Study personnel will perform orthostatic BP and HR measurements.
14. Study personnel blinded to the study will give the participant the study drug vs placebo drug with a glass of water, according to the randomized, double-blind, placebo-control crossover design of this study.
15. Study subject will be asked to rest in sedentary or recumbent position for 3 hours.
16. CRTU Staff will do blood draw #2 after 30 minutes of supine resting, 3 hours after intake of active drug/placebo drug.
17. The 12-lead ECG recording continues on.
18. Study personnel will perform post-intervention paced breathing test, details described in the IRB Protocol. Breathing will be measured by elastic bands around the chest and abdomen.
19. Post intervention endothelial function test will be performed by the study team.
20. Post intervention ultrasound of the heart may be performed by the study team or echo lab personnel.
21. Study personnel will perform orthostatic BP and HR measurements.

22. Study personnel will describe the series of stress tests that will follow and BP, HR, ECG measurements will continue through the stress tests.
23. Study personnel will perform series of stress tests (physical, mental, and cold stress), details described in the IRB Protocol. During the stress tests continuous BP, HR and 12-lead ECG data will be recorded and will continue to be recorded the recovery time periods.

Participants will be allowed to eat, selecting meals from a prepared menu.

24. Study subjects will be scheduled a follow up appointment in the CRTU to be done within 2 months (minimum 5 days apart) but at the same time of the day; and will be dismissed home for the day.

6.2 Visit 2

CRTU Day # 2

1. Subjects report to SMH CRTU at the already pre-scheduled appointment time. Participants should not eat at least 4 hours prior to coming to CRTU. Participant is reminded to avoid all stimulants including caffeine and alcohol 24 hours prior to the study.
2. CRTU personnel informs study personnel when the subject arrives at the CRTU.
3. Study personnel explain the research plan for day #2 and answers any questions the participant may have.
4. CRTU personnel will obtain height and weight of the participant. CRTU personnel performs urine pregnancy test as needed (Urine collection #2). If the participant is pregnant, then the participant is unable to participate in the study, and will receive \$25.00 for their time. In all participants at least 100 ml of urine may be collected for future biomarker analysis at baseline and
5. Participant will be asked to fill out the following questionnaires on a Mayo laptop or on paper. Some of these questionnaires may be administered more than once: Food Scale, Symptoms Questionnaire, and Sleepiness Scales.
6. CRTU Staff will insert peripheral IV line into the forearm and blood draw #1 will be obtained after at least 30 minute rest.
7. Study personnel will obtain BP and HR measurements in supine position. Measurements will be taken every 1-3 minutes throughout the study.
8. Study personnel will be obtaining 12-lead ECG recording throughout the study.

9. Study personnel will perform paced breathing test, details described in the IRB Protocol. Breathing will be measured by elastic bands around the chest and abdomen.
10. Baseline endothelial function test will be performed by the study team.
11. Study personnel will perform orthostatic BP and HR measurements.
12. Study personnel blinded to the study will give the participant the study drug vs placebo drug (one not received on Day 1), according to the randomized, double-blind, placebo-control crossover design of this study.
13. Study subject will be asked to rest in sedentary or recumbent position for 3 hours.
14. CRTU Staff will do blood draw #2 after 30 minutes of supine resting at 3 hours after intake of active drug/placebo drug.
15. The 12-lead ECG recording continues on.
16. Study personnel will perform post-intervention paced breathing test, details described in the IRB Protocol. Breathing will be measured by a elastic bands around the chest and abdomen.
17. Post intervention endothelial function test will be performed by the study team.
18. Post intervention ultrasound of the heart may be performed by the study team or echo lab personnel..
19. Study personnel will perform orthostatic BP and HR measurements.
20. Study personnel will describe the series of stress tests that will follow and BP, HR, ECG measurements will continue through the stress tests.
21. Study personnel will perform series of stress tests (physical, mental, and cold stress), details described in the IRB Protocol. During the stress tests continuous BP, HR and 12-lead ECG data will be recorded and will continue to be recorded over the recovery time period.
22. Participants will be allowed to eat, selecting meals from a prepared menu.
23. Participant completes the study and will receive \$200 if both study days are completed. If participants did only one day of this protocol, they will be paid \$80

During this study, the participants will take part in the following studies:

1. Medical history interview and completion of questionnaires: This involves answering questions about past and present medical, family history, sleep habits, and social history including intake of stimulants. Questionnaires used are: Cardiovascular Research Data Sheet, Stimulant Intake Questionnaire, Berlin Questionnaire, Sleep Breakfast Questionnaire, Food Scale, Adult ADHD Self Report Checklist, Symptoms Questionnaire and Sleepiness Scales.
2. Baseline body composition measurements: This involves measurements of height, weight, neck, arm, waist and hip circumferences. Bioimpedance measurement- It involves attaching 2 pairs of electrodes – one on the foot and one on the hand. A small electrical current is used to determine resistance and reactance to evaluate body composition. Although there are no known harmful effects of the small electrical current, as a precaution, this measurement will not be done on those subjects that have an implanted device such as a pacemaker, defibrillator, or infusion pump, etc., or any other implanted device.
3. Blood pressure and heart rate measurements: This involves having a BP cuff inflated around the arm at periodic intervals in standing and lying positions. Heart rate will be measured at the time of BP measurement. Measurements will be taken at regular intervals.
4. 12-lead ECG recording: A set of electrodes will be attached to the skin on the chest and ECG tracing will be obtained in lying position throughout the study.
5. Blood samples: A peripheral IV catheter will be inserted into patient's forearm to obtain blood samples and will be kept until the end of the day study. Samples will be obtained at baseline and after study drug/placebo drug administration during supine rest. About 1/2 cup of blood will be drawn with each blood draw to measure cardiovascular markers. Blood samples will be stored safely for future studies of serum markers and will be given a code.
6. Paced Breathing: This involves measurements of HR variability and baroreflex sensitivity to enable better characterization of cardiometabolic changes done before and after drug intake. Subjects will undergo detailed training to perform spontaneous and controlled breathing tests in the supine position. Continuous non-invasive blood pressure will be monitored during this test using a small finger BP cuff. Breathing will be measured by elastic bands around the chest and abdomen.
7. Stress response: The effects of study drug/placebo drug on cardiovascular/circulatory response to stress stimuli will be also studied. Stress tests (sustained handgrip, mental stress, and the cold pressor test) will be conducted in a sequential fashion and continuous BP and HR measurements will be done. Mental stress will be conducted by asking the subjects to complete serial mathematical tasks as fast as possible for three minutes. Physical stress, isometric hand grip performed with a dynamometer and by asking the subjects to sustain a handgrip of one-third of their maximum voluntary hand grip contraction maintained for 2 minutes. The cold pressor test requires subjects to place one hand into an ice water for three minutes up to the level of the wrist. The cold pressor test will be performed always last because of sustained effects of the test. Throughout all tests, measurements of BP, HR, ECG and SpO₂ will be obtained.
8. Ultrasound of the heart and arm vessel: Ultrasound assessment of heart and flow-mediated vasodilation (FMD) of the brachial artery will be performed. B-mode images and Doppler flow

will be collected to estimate brachial artery diameter and blood flow velocity. After baseline measures, reactive hyperemia will be induced by the inflation of a BP cuff placed around the forearm to a pressure of 50 mmHg above SBP (to a maximum of 200 mmHg) for 5 minutes, followed by release. Brachial artery diameter and flow velocity will be measured after deflation to measure FMD and shear stress rate.

9. Food/Diet monitoring: At the end of the study day, subjects will be given a menu of food options and will be asked to select the foods they wish to eat. The menu will be consistent for all subjects and include low fat, high fiber foods as well as high fat, high sugar and high sodium foods. The food will be weighed by specially trained staff from the team of dieticians. Subjects will be allowed to order and consume as much food as desired. When done eating, the tray of food, including leftovers, will be removed. We will record their appetite level, selection of foods, and actual amount of consumption of food. Leftovers will be weighed and the nutrient analysis will be calculated for the actual food intake using ProNutra software. The analysis will include Calories, Protein, Fat, Carbohydrate, Fiber, and Sodium as well as total weight of the food and beverages served. A consistent menu will be offered and the same procedure will be followed after subjects receive placebo vs. Adderall.
10. Urine sample: At least 100 ml of urine will be collected for future biomarker analysis with each urine collection.

7 Statistical Plan

